5.2 Storage and Handling

Individual vials of VAX102 vaccine and diluent (F105) will be provided by VaxInnate Corp. The VAX102 vials and diluent should be stored at a controlled temperature ($\leq -60^{\circ}\text{C}$) in a secured freezer until use. On each dosing day, VAX102 vials and diluent required for vaccinating the subjects should be removed from the freezer and placed at room temperature until visibly thawed (~ 15 minutes) prior to dosing or diluting by the investigational pharmacist or trained study personnel. The vaccine or diluent in each vial will be inspected to ensure that it is completely thawed and then gently swirled by the investigational pharmacist or trained study personnel to ensure it is thoroughly mixed prior to it being drawn into a syringe for compounding or for injection into a study subject. All vials removed from the freezer should be used within 2 hours and must NOT be re-frozen and NOT used thereafter. After each dose preparation, the pharmacist will place the used vial(s) in a kit box, seal the kit box with a label with the subject's randomization number and store at room temperature.

FLUVIRIN® will be supplied as 5 mL multi-dose vials to study sites and stored under manufacturer's instructions.

5.3 Investigational Product Preparation

On Study Day 0, the investigational pharmacist or trained study personnel will be provided with each eligible and consenting subject's initials, subject ID number (SID), and gender by the study site's personnel. The investigational pharmacist or trained study personnel will use the list to determine the Group and treatment assignment. The investigational pharmacist or trained study personnel will prepare two labels bearing the subject's SID number, initials, date, and **vaccine 1** or **vaccine 2**. The label with **vaccine 1** will be affixed to the **TIV vaccine syringe**, and the label with **vaccine 2** will be affixed to the **VAX102 vaccine syringe**. The subject's SID number and randomization number will be transcribed onto the Investigational Product Accountability Log.

The investigational pharmacist or trained study personnel will then prepare the appropriate study vaccine dose dilution for each subject.

The one clinical dose of STF2.4xM2e(Hu) (VAX102) will be achieved as described below **Section 5.3.1**. Each vial of vaccine contains 0.75 mL of vaccine at a concentration of 20 ug/mL. Each vial of vaccine diluent contains 1.8 mL.

The placebo (F105) will be achieved as described below in **Section 5.3.2**.

The 0.5 ml dose of **FLUVIRIN®** will be achieved as described below in **Section 5.3.3**.

After study vaccine preparation is completed for a given day, any opened stock vaccine vials will be restoppered and retained for review by a VaxInnate representative, sent to VaxInnate or destroyed as per site's standard operating procedure.

5.3.1 VAX102 Vaccine Dilution Scheme Group A Dose 1.0 µg for 0.5 mL volume for IM Injection

For all dilutions use 0.3 mL Lo-Dose syringe

1. Remove 0.20 mL from the 20 µg/mL vaccine vial. Dispense the entire volume into the vial of F105 diluent. The final volume is 2.0 mL (0.2 + 1.8 mL) at 2.0 µg/mL.
2. Inject 0.50 mL IM of this 2.0 µg/mL solution to deliver 1.0 µg VAX102.

5.3.2 Placebo (F105) Group B for 0.5 mL volume for IM Injection

NO DILUTION NEEDED

1. Remove 0.5 mL from the F105 diluent vial.

5.3.3 TIV Vaccine for Groups A-B STD for 0.5 mL volume for IM Injection

NO DILUTION NEEDED

1. Remove 0.5 mL from FLUVIRIN® vial for injection of influenza virus hemagglutinin (HA) from 3 strains.

5.4 Investigational Product Administration

All investigational products are to be administered under the supervision of the Principal Investigator or a qualified subinvestigator designated to VaxInnate in writing prior to the trial and trained in both the protocol and contents of the Investigator's Brochure. Under no circumstances will the Principal Investigator allow investigational products to be used other than as directed by this protocol.

Investigational products will be administered as follows:

Study vaccines will be prepared as described in **Section 5.3** and administered within two (2) hours of dilution.

Administration of the vaccine in all parts of the study will be intramuscular injection into the deltoid muscle region by **a 1 inch 23 gauge needle and 1 mL syringe on Day 0**. In all vaccinations a standard dose of TIV IM will be administered first followed by VAX102 or Placebo [F105]. Both vaccinations will be given into the non-dominant arm of each subject. The arm used (right or left) will be recorded in the subject's case report form (CRF). Each site should be wiped with an alcohol wipe before injection of the vaccine. The times when the subjects' vaccinations were given should be recorded in the CRF. At the time of vaccine preparation, duplicate labels will be prepared that contain the subject ID number, initials, date, and **vaccine 1** and **vaccine 2**. These labels will be attached to or accompany the filled syringes. One of the labels will be removed and attached to the subject's Case Report Form for verification of correct dose.

5.5 Accountability of Investigational Products

The Principal Investigator or a designee is responsible for maintaining complete investigational products inventory records accounting for receipt, storage, dispensation, and final disposition using forms supplied by (or local equivalents approved by) VaxInnate or designee. These records will be reviewed by VaxInnate representatives. At the conclusion of the trial all vials of investigational products, used and unused, will be returned to VaxInnate or destroyed as per site's SOP only after VaxInnate's approval.

6 STUDY SCHEDULE

The site will recruit the subjects and designated site personnel will perform all procedures according to the protocol.

6.1 Screening Visit (day -30 to -1)

The following procedures will be done at the indicated times (see also **Appendix C** for a Schedule of Procedures and Assessments).

- Potential subjects will be instructed in the nature of the study, the intended procedures, and risks and benefits of study participation. Questions will be solicited. Signed and dated written, informed consent will be obtained and persons not giving consent will not participate further.
- Inclusion and exclusion criteria will be reviewed to assure subject eligibility.
- Demographics and a medical history will be obtained and documented.
- A complete baseline physical examination (HEENT, heart, lungs, abdomen, skin, lymph nodes, neurological, musculoskeletal systems), height and weight including vital signs (heart rate [HR], blood pressure [BP], respiratory rate [RR], oral temperature [Temp]), will be performed and recorded at this visit.
- Subjects eligible by history will provide approximately 20 mL of venous blood and a urine sample will be used for baseline clinical laboratory tests:
 - Hematology: complete blood count (CBC) including hemoglobin (Hgb), hematocrit (Hct), white blood cell (WBC) with differential, and platelet count
 - Chemistry: serum SGPT/ALT and SGOT/AST, blood urea nitrogen (BUN), creatinine, glucose,
 - Urinalysis: glucose, protein, blood via multistix or equivalent dipstick (trace protein is acceptable),
 - In females of childbearing potential, a negative urine pregnancy test
- Subjects will be asked to provide phone contact information.

6.2 Dosing and Early Follow-up

6.2.1 Day 0 Vaccination

Pre-Dosing

- An interval medical history will be performed to ensure that each subject continues to meet all inclusion and no exclusion criteria.
- Vital signs (HR, BP, RR, Temp) will be obtained and recorded.
- A targeted physical examination of axillary lymph nodes, injection site evaluation, and baseline sign and symptom assessment will be performed and recorded by qualified study personnel. Other body system examination will be performed and recorded, if directed by subject's symptoms, by qualified NP, PA, or physician.
- Approximately 10 mL of venous blood will be evaluated for serology (serum M2e and flagellin antibody tests) and Hemagglutination inhibition assay (HAI).
- Approximately 5 mL of venous blood will be evaluated for C-reactive protein (CRP).
- A urine specimen will be collected from each female subject of childbearing potential and tested in the clinic for evidence of pregnancy. No test article will be administered until a negative result is obtained and documented.

Prime Dosing and 30-Minute (+15) Follow-up

On day of vaccination, study subjects will remain in clinic for observation for a minimum of 30 minutes post vaccination or longer as directed by study physician or designate.

- TIV (Vaccine 1) followed by VAX102 or Placebo (Vaccine 2) will be administered IM as described in **Section 5.4**. (*Subjects who receive any amount of test article will be considered enrolled and followed through Day 28 (± 2) for safety and immunogenicity. No additional follow-up will be required of subjects who are screened but do not receive any test article.*)
- At 30 minutes (+15 minutes) after dosing, each subject will have the following:
 - vital signs (HR, BP, RR, Temp),
 - targeted assessment of axillary lymph nodes and site of injection performed by qualified study personnel and recorded. Other body system examination will be performed and recorded, if directed by subject's symptoms, by qualified study personnel. New abnormalities will be captured as adverse events and any medications taken captured on concomitant medications.
- Subject will be provided with a Memory Aid, ruler and a digital thermometer, and instructed on their use. In the clinic the subjects will take his/her temperature orally and measure the injection site area of pain and/or induration. The Memory Aid will be used from Day 0 to Day 6.
- Subjects will be instructed to return for the Day 1 clinic visit.

6.2.2 Day 1 (+1)

- Vital signs (HR, BP, RR, Temp) will be taken and recorded.
- Subjects will be queried regarding the occurrence of adverse events, Memory Aid reviewed (if available) and any new concomitant medications taken, and the results recorded.

- A targeted assessment of axillary lymph nodes and site of injection will be performed by qualified study personnel and recorded. Other body system examination will be performed and recorded, if directed by subject's symptoms, by qualified personnel. New abnormalities will be captured as adverse events.
- Approximately 20 mL of venous blood will be evaluated for the following laboratory tests:
 - Hematology: complete blood count (CBC) including hemoglobin (Hgb), hematocrit (Hct), white blood cell (WBC) with differential, and platelet count
 - Chemistry: serum SGPT/ALT and SGOT/AST, blood urea nitrogen (BUN), creatinine, glucose
 - C-reactive protein (CRP)
- Subjects will be instructed to return for the Day 14 (± 2) clinic visit and bring back their Memory Aid.

6.2.3 Day 14 (± 2)

- Vital signs (HR, BP, RR, Temp) will be taken and recorded.
- Subjects will be queried regarding the occurrence of adverse events, Memory Aid reviewed and retained, and any new concomitant medications taken, and the results recorded.
- A targeted assessment of axillary lymph nodes and site of injection will be performed by qualified study personnel and recorded. Other body system examination will be performed and recorded, if directed by subject's symptoms, by qualified personnel. New abnormalities will be captured as adverse events.
- Approximately 10 mL will be evaluated for serology (serum M2e, flagellin and HAI antibody tests).

6.2.4 Day 28 (± 2)

- Vital signs (HR, BP, RR, Temp) will be taken and recorded.
- Subjects will be queried regarding the occurrence of adverse events, any new concomitant medications taken, and the results recorded.
- A targeted assessment of axillary lymph nodes and site of injection will be performed by qualified study personnel and recorded. Other body system examination will be performed and recorded, if directed by subject's symptoms, by qualified personnel. New abnormalities will be captured as adverse events.
- Approximately 10 mL will be evaluated for serology (serum M2e, flagellin and HAI antibody tests).
- This contact completes subjects' formal participation in protocol VAX102-07.

6.2.5 Unscheduled Visit

At anytime during the course of this study between scheduled clinic visits, the study subject will be asked to initiate a call to the study staff to report any concerning symptoms.

- This study subject will be interviewed by a clinical study team member and any subjects who report moderate (Grade 2) or greater symptoms will be considered for a visit for further evaluation.

Evaluation will include:

- Vital signs (HR, BP, RR, Temp) will be taken and recorded.
- Subjects will be queried regarding the episode of illness and any concomitant medications taken, and the results recorded as adverse event(s).
- A targeted physical examination directed by subject's symptoms will be performed. New abnormalities will be captured as adverse events.
- If symptoms as suspected by the investigator are more serious, the subject will be referred to his/her primary care physician or local emergency room for further evaluation and treatment.

Refer to Section 4.6 for Early Withdrawals or Discontinuations.

7 STUDY PROCEDURES AND EVALUATIONS

7.1 Clinical Procedures and Evaluations

7.1.1 Screening

Subjects will be invited to give written informed consent after having the protocol described to them, review inclusion/exclusion criteria and being given the opportunity to read the consent form, and having their questions answered. During the screening visit, consenting subjects will have his/her medical history confirmed and selected clinical laboratory tests to ensure eligibility. Those subjects remaining eligible after evaluation of screening clinical laboratory values will return on Day 0 for review of eligibility and for vaccination.

7.1.2 Medical History and Physical Examination

A complete physical examination (HEENT, heart, lungs, abdomen, skin, lymph nodes, neurological, musculoskeletal systems) (screening visit days -30 to -1) and medical history/review of systems will be performed and recorded before the first dosing (prime).

The medical history should record significant problems active at the time of screening or within the prior year. Problems that have been clinically inactive within the prior year, but which might alter the subject's current or future medical management, should also be noted (e.g., known mitral valve prolapse, history of seizure disorder, etc.). Completely resolved past problems with no impact on current medical management (e.g., a healed fracture at age 12) may be omitted.

Vital signs (HR, BP, RR, oral Temp) will be included in the physical examination, and any significant abnormalities in the physical examination will be recorded on the case report forms.

7.1.3 Targeted Physical Examination, Baseline Signs and Symptoms, and Injection Site Assessment, and Vital Signs Before and/or After Vaccination

A targeted physical examination to include assessment of axillary lymph nodes, injection site evaluation, and vital signs will be obtained and recorded at Day 0 before vaccination, 30 minutes after vaccination, and on Days 1, 14 (± 2), and 28 (± 2), and unscheduled visits, if applicable.

Targeted physical examinations as needed for evaluation of complaints during the trial may be performed at the discretion of the investigator. These examinations may include any other body system directed by subject's symptoms and will be recorded using a standardized worksheet. Any new abnormalities will be captured as adverse events.

7.1.4 Safety and Tolerability Evaluation

Following vaccination, each subject will maintain a written Memory Aid of potential vaccine reactogenicity for seven (7) days after vaccination (Days 0 - 6). Subjects will be asked to return the Memory Aid at Day 1 for review if available and on Day 14 with abstraction of the data from the Memory Aid at that time.

Clinical laboratory studies will be performed at screening and at Day 1 (+1).

Ascertainment of adverse events and new or changes in concomitant medications will be carried out at each visit through early termination or study completion Day 28 (± 2).

Specific definitions and grading for vaccine reactogenicity symptoms and findings and adverse events are outlined in later sections and related appendices. Subjects will be followed until resolution of adverse events or until their clinical status has clearly stabilized and will be referred to their local physician for any unresolved issues.

7.1.5 Concomitant Medications

Subjects should be instructed not to introduce new medications without consulting or notifying the investigator or his designee. Subjects will be questioned regarding new medications at each visit through Day 28 (± 2) days. Any such medications will be recorded on the case report form, and also utilized by site staff as a prompt to query the subject regarding potential adverse events triggering changes in concomitant medications.

7.2 Laboratory Evaluations

7.2.1 Clinical Laboratories

Hematology: The following will be done at the screening visit and Day 1 after vaccination.

- Complete blood count (CBC) including hemoglobin (Hgb), hematocrit (Hct)
- White blood cell count (WBC) with differential,
- Platelet count

Clinical Chemistry: The following will be done at the screening visit and Day 1 after vaccination.

- SGPT/ALT and SGOT/AST
- Blood urea nitrogen (BUN)
- Creatinine
- Glucose

CRP will be done before vaccination on day 0 and Day 1 after vaccination.

Urinalysis: A urine sample will be obtained at the screening visit and if clinically indicated to evaluate illness at any other time. The following will be tested in the clinical laboratory:

- Glucose
- Protein
- Hemoglobin

Urinalysis with a multistix or equivalent dipstick is acceptable.

Pregnancy Testing: Urine β -HCG determination will be performed on a freshly-obtained urine specimen on the day of screening and on Day 0 prior to vaccination on each female subject of child bearing potential. A negative result must be obtained and recorded before any test article is administered.

7.2.2 Specific Antibody Assays

A venous blood sample (approximately 10 mL) will be taken from each subject pre-vaccination on Day 0 and on Days 14 and 28 for the analysis of anti-M2e serum antibody titers and HAI antibodies.

The immunogenicity of the VAX102 vaccine will be evaluated by measuring the number of subjects who demonstrate seroconversion either by developing a measurable titer following vaccination or by showing a significant increase in anti-M2e serum antibody titers post-vaccination. Standard statistical tests will be used to define a significant rise in antibody titers.

In addition to HAI titers (H1, H3 and B components), sera Days 0, 14 (± 2) and 28 (± 2) will also be evaluated for microneutralization titers, anti-flagellin titers using a panel of exploratory assays.

7.2.3 Specimen Collection, Preparation, Handling, and Shipping

The instructions for handling each type of specimen are found in the laboratory instructions or procedures.

8 ASSESSMENT OF SAFETY

8.1 Definition of Immediate Complaints, Vaccine Reactogenicity and Adverse Events

8.1.1 Immediate Complaints

Immediate complaints as a result of vaccination (see **Appendix A**) are recorded on the symptom assessment CRF after 30 minutes of observation. The Memory Aid given to the subject will be used to capture symptoms for the next 7 days. The Memory Aid provides uniform definitions for grading severity.

8.1.2 Vaccine Reactogenicity

A selection of subjective complaints (see **Appendix A**) reasonably anticipated to occur as a result of receipt of the test articles are provided in the Memory Aid. These will be solicited and recorded by the subject. A selection of potential physical findings that might occur as a result of vaccination is provided on the Targeted Physical Assessment. Findings from these two sources will be abstracted to the case report forms and reported as vaccine reactogenicity. These findings should NOT be additionally recorded as adverse events unless they fulfill the criteria set forth in **Section 8.1.5**.

Severity definitions used to grade reactogenicity events are included as part of the Targeted Physical Assessment and Memory Aid. Subjects will record at the level of greatest severity of each reaction type experienced each day during the seven-day post each vaccination interval. Counts and proportions of study vaccine recipients reporting each class of solicited reaction in the first seven days post vaccination will be summarized by severity grade, and by all non-zero severity grades.

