8.1.5 Double Reporting of Reactogenicity Findings/Complaints

As per sections 8.1.1, and 8.1.2 above, findings and/or complaints specifically captured by the Memory Aid should NOT, in general, be additionally recorded as AEs if they occur within seven (7) days of a study vaccine dose.

The rationale for not doubly-reporting reactogenicity events as AEs is as follows. The specified range of reactogenicity complaints and findings are those reasonably expected to be associated with IM influenza vaccine. These data are collected by clinical study team member(s) and transferred to CRFs, analyzed, and reported in detail to investigators and regulatory authorities as *vaccine reactions* and are *presumed to be product-related*. Separation of these numerically frequent, but usually minor, vaccine reactions from other classes of adverse events has two benefits to the safety analysis. It markedly simplifies the careful analysis of the frequency and duration of these reactions and their comparison among treatment groups. In addition, these reports would, if reported as routine AEs, tend to cluster in a few MedDRA body systems. Separating these common, expected vaccine reactions from other AEs allows for the elucidation of other potentially important, but less common, types of events in the statistical analysis of AEs in those body systems.

There are *three exceptions* to the rule regarding double reporting:

- a) Any of these findings or complaints which fulfills the definition of “Serious Adverse Event” (see **Section 8.2**) should be recorded as an AE (and reported as per **Section 8.3**),
- b) Any of these findings or complaints that persists beyond seven (7) days after a study vaccine dose should be recorded as an AE,
- c) Any of these findings or complaints which the investigator *unequivocally* categorizes, based on strong clinical evidence, as unrelated to the test article should be recorded as an AE. In this case the investigator *must* assign a causality of “unrelated” (not “unknown”) and record a clear rationale in source documents.

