9.2.10.2 Reactogenicity and other AEs

Volunteered, observed, and elicited AEs will be recorded from the time of the vaccination through the Day 28 (± 2) follow-up visit. AEs will be coded using MedDRA (Medical Dictionary for Regulatory Activities). In MedDRA, each reported event is mapped to a Lowest Level Term (LLT), a Preferred Term (PT), and a System Organ Class (SOC). A treatment-emergent AE will be defined as an AE that was not present prior to vaccination or was present but worsened in intensity or frequency after vaccination.

Tabulations of solicited AEs will be produced for immediate reactogenicity events that occur within the first 30 minutes of each vaccination, and separately for those that begin within 7 days of vaccination. All solicited reactions will be considered causally related to vaccination. Causality of all other AEs will be assessed by the investigator, as noted in **Sections 8.1.4** and **8.1.5**. AEs other than reactogenicity will be tabulated for several time periods: from baseline through Day 28 (± 2). Subject incidence will be summarized, therefore, each subject contributes only once to each preferred term or to a SOC. AE summaries will also be produced for events that are considered at least possibly related to study treatment, and for events of at least severe intensity. A statistical analysis for trend in increasing rates with increasing dose will be performed by the Cochran-Armitage trend test. Fisher's Exact test will be used to assess the significance of the difference in rates between the overall active vaccination group(s).

All reported AEs (treatment-emergent or not) will be listed. Listings will include study day, duration (days), relationship to treatment, severity, action taken, outcome, and whether or not serious criteria apply. Treatment-emergent AEs will be summarized, overall and by severity and relationship to treatment. For each SOC and PT within SOCs, the numbers and percentages of subjects reporting an event will be calculated. Similar listings and summaries will be done separately for reactogenicity and serious AEs.

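### Sections 8.1.2 and 9.2.10.2 count solicited reactions by different rules, and neither expressly uses the Day 0 pre-dose symptom assessment; the effect on systemic reactogenicity is modest

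*Protocol*

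**What the plan says.** Four parts of the protocol bear on this.

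- **Section 8.1.2** gives the reactogenicity summary: counts and proportions of subjects "reporting each class of solicited reaction in the first seven days post vaccination will be summarized by severity grade, and by all non-zero severity grades". The test is whether the symptom is reported in the window. Onset and pre-dose grade play no part.
- **Section 9.2.10.2** describes the tabulation differently. Apart from the events in the first 30 minutes, solicited events are tabulated "separately for those that begin within 7 days of vaccination". The next sentence is "All solicited reactions will be considered causally related to vaccination". Section 8.1.5 agrees, calling such reactions "presumed to be product-related".
- **Section 9.2.10.2** also has a definition that refers to baseline, for treatment-emergent AEs: an "AE that was not present prior to vaccination or was present but worsened in intensity or frequency after vaccination". Sections 8.1.2, 8.1.3 and 8.1.5 generally keep solicited symptoms of the first seven days out of the AE record.
- **Section 6.2.1** has a pre-dose step on Day 0 in which "injection site evaluation, and baseline sign and symptom assessment will be performed and recorded by qualified study personnel". Appendix C lists it too. No grading scale is given for it, and section 9 does not mention its use.

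**The concern.** Entry does not bar a subject with a mild headache, tiredness or an aching joint on Day 0. Section 4.3 excludes active infection, an oral temperature of 38 °C or more, and significant illness. Some subjects may therefore carry a Grade 1 systemic symptom into the Memory Aid period. Whether such a subject is a reactor depends on which section the programmer follows.

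Reactogenicity is part of the primary objective. Under 8.1.2, carried-over symptoms raise the any-grade rate in both arms, and the Grade 1 row with it. They are then deemed caused by vaccination, and the difference between arms shrinks. Under the onset rule the error can run the other way, because a symptom that was already present and became worse did not begin after the dose.

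**Working it through.** **1. The rules side by side.** Three hypothetical headache records:

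| Pre-dose grade | Grade after dosing | 8.1.2 (reported, any non-zero) | 9.2.10.2 solicited table (onset) | 9.2.10.2 treatment-emergent (new or worsened) |
|---|---|---|---|---|
| 1 | 1 on Days 0–2 | counted | not counted | not counted |
| 1 | 3 on Day 1 | counted, as Grade 3 | not counted, read literally | counted |
| 0 | 1 on Day 1 | counted | counted | counted |

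The rules agree only on the third record. The last column is written for AEs and is not expressly applied to solicited reactions.

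**2. Inputs for the size.** The protocol states no effect size, alpha or power for reactogenicity, and 9.2.2 calls the sample size arbitrary. There is no figure to reproduce, so this is an illustration.

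- Group size: 40 per arm (section 4.1).
- Any systemic symptom, from the protocol's Table 2: 1 µg, 18 − 6 = 12 of 18, p₁ = 66.7%; placebo, 16 − 9 = 7 of 16, p₀ = 43.8%. Difference 22.9 points.
- Assumed, not in the documents: share q with a systemic symptom before dosing of 5%, 10% or 20%; 80% of these persist into the Memory Aid; independence from new onset; two-sided alpha 0.05.

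**3. Formula.** Counted rate = p + (1 − p) × 0.8q. The counted difference is therefore (p₁ − p₀) × (1 − 0.8q). Power is by exact enumeration of Fisher's test at 40 v 40.

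| q | 0.8q | 1 µg rate | Placebo rate | Difference (points) | Fisher power |
|---|---|---|---|---|---|
| 0 | 0 | 66.7% | 43.8% | 22.9 | 47% |
| 5% | 4% | 68.0% | 46.0% | 22.0 | 44% |
| 10% | 8% | 69.3% | 48.3% | 21.1 | 41% |
| 20% | 16% | 72.0% | 52.8% | 19.2 | 34% |

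**4. Extra reactors among 80.** This is 40 × 0.8q × [(1 − p₁) + (1 − p₀)] = 40 × 0.8q × (0.333 + 0.5625). It gives 1.4, 2.9 and 5.7 subjects, or about 1, 3 and 6.

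**5. Sensitivity.**

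- With full persistence the difference is 20.6 points and power 39% at q = 10%; at q = 20% they are 18.3 points and 32%.
- Table 2 may already include carried-over symptoms. Removing 10% at full persistence, (p − 0.1)/0.9, gives 63.0% v 37.5%, a difference of 25.5 points and power of 57%. The direction is the same.
- Local reactions in Table 2 are 15/18 v 5/16, or 83.3% v 31.3%. Even with 10% carry-over at full persistence, Fisher power stays at 99%, and pre-dose injection-site findings are unlikely anyway.

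**The case against.** The strongest reply is that section 9.2.10.2 already deals with the matter. Its onset wording leaves an unchanged pre-existing symptom out of the seven-day table. The section covers reactogenicity together with other AEs, calls the solicited events AEs, defines treatment emergence, and says that similar summaries will be made for reactogenicity. On that reading new-or-worsened already governs, and how the baseline enters the tables is detail for the statistical analysis plan.

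Part of this stands. A reader might infer from 8.1.2 alone that pre-existing symptoms will simply become related reactions in the analysis. The documents do not support that, since one of the two stated rules excludes unchanged symptoms. But the treatment-emergent reading is an inference, and it sits badly with the onset wording a few lines away, which does not allow for worsening. Two stated rules that disagree are a defect of the protocol, whatever a later plan adds. The route in 8.1.5(c) for clearly unrelated findings does not settle it either: an event recorded that way is still reported as reactogenicity as well.

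Other limits also stand:

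- A reader might infer that the onset rule hides severe worsening. It does not disappear: 8.1.2 also summarises by grade, so a Grade 3 headache shows there.
- A reader might infer a loss of planned power on a primary contrast. No primary reactogenicity endpoint, test or power is named. Section 9.2.10.2 gives Fisher's test for rates without an alpha. Randomisation balances background symptoms in expectation.
- A reader might take 0.8q, that is 4, 8 or 16 points (3, 6 or 13 of 80 subjects), as added reactors. That is gross carry-over. Many of those subjects would have reacted anyway, and the net figure is about 1, 3 or 6.

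**Conclusion.** The point holds as a conflict between two stated counting rules, with a pre-dose assessment that neither expressly uses. It does not depend on any prevalence. Its size does: over the assumed range, about 1 to 6 extra systemic reactors of 80, a loss of 0.9 to 3.7 points from a 22.9-point difference, and Fisher power down from 47% to between 44% and 34%. These figures are illustrative. Prevalence, persistence and alpha are assumed, and the Table 2 rates come from groups of 18 and 16 given VAX102 or placebo without TIV. Entry of healthy volunteers without active infection or fever should keep the true prevalence low. Local reactions are hardly affected. It is a modest fault that is cheap to correct.

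**What to change.** Use one definition in 8.1.2 and 9.2.10.2 for the between-group tabulation: a solicited reaction is a symptom absent at the Day 0 pre-dose assessment, or present then and of higher grade within the seven days after vaccination. Let it replace the onset wording in 9.2.10.2. State in 6.2.1 that the pre-dose assessment is recorded on the Memory Aid grading scale, since an ungraded baseline cannot show worsening and cannot be recovered later. Keep the table of all reported symptoms regardless of baseline alongside, so that nothing is lost from the safety record.

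The cost is wording in two sections, one grading instruction and one extra table. No visit or sample is added, because the assessment is already scheduled. The headline reaction rates will be slightly lower than under 8.1.2 as written, and the unadjusted table shows by how much.
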